## APPENDIX D. ANALYSIS OF NON-NORMAL ENDPOINTS

### D.1. Analysis of Binary Endpoints

This section describes the methods for analyzing other binary endpoints.

For each binary endpoint, a 95% confidence interval will be calculated for each proportion by treatment group using the Clopper-Pearson method [Clopper, 1934].

For analyses conducted in the randomized population, the weighted difference in proportions between treatment groups, adjusting for the stratification factors, and the corresponding 2-sided 95% confidence interval will be calculated by weighting according to the Mantel-Haenszel method. The associated odds ratio and corresponding 2-sided 95% confidence interval will also be calculated. Subgroup analysis will be conducted similarly.

The below efficacy endpoints have binary outcome measures and will use the code structure presented in [Exhibit D 1](#). For the first 4 endpoint, noninferiority will have been established if the lower limit of the confidence interval for the risk difference is above -15%.

- At least 1 Hb value in the geography-specific target range in Weeks 24 to 36
- At least 1 Hb value in the geography-specific target range in Weeks 40 to 52
- Hb values in the geography-specific target range for at least 1/2 of the observations in Weeks 24 to 36
- Hb values in the geography-specific target range for at least 1/2 of the observations in Weeks 40 to 52
- Hb increase of >1.0 g/dL in Year 1 (CI-0014)
- Receipt of at least 1 administration of elemental iron, repeated using each route, intravenous (IV), or oral
- Receipt of any red blood cell (RBC) transfusion
- Receipt of any erythropoietin-stimulating agent (ESA) rescue medication
- Receipt of any rescue therapy (series of definitions from narrow to broad)
- Hb values >12, 13, or 14 g/dL
- Hb values <8 or 9 g/dL
- Hb increase of >1.0 g/dL within any 2-week period (CI-0015)
- Hb increase of >2.0 g/dL within any four-week period (CI-0015)

#### Exhibit D 1. SAS Code for Analyzing Binary Endpoints

---

```
proc freq data=&OUTDAT2.;
  tables STRAT1*STRAT2*STRAT3*TRT*&OUTCOME/riskdiff(common) cmh;
  ods output CommonPdiff=CommonPdiff;
run;
```

---

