## 1 INTRODUCTION

This statistical analysis plan (SAP) covers the two PRO2TECT studies, Protocols AKB-6548-CI-0014 and AKB-6548-CI-0015, hereafter referred to as CI-0014 and CI-0015, respectively.

The SAP supports the Statistical Methods Section of the clinical study reports (CSRs). It elaborates upon the protocol-specified endpoint definitions and the formal statistical methods that will be used in analyzing both studies. Unless otherwise specified, all analyses will be conducted for each study separately.

Throughout this SAP, planned analyses of both studies are identical to each other except in those places that specifically identify where the plans diverge. Akebia does not intend to pool data together for formal efficacy and general safety analyses; however, analyses of major adverse cardiovascular events (MACE) will be pooled from both studies. A separate SAP will describe the planned methodology for the MACE analyses.

If the analyses described in the protocols differ from those in this SAP, the methods of the SAP prevail.

This SAP contains language and programming code that specifies the exact intent of each analysis. The sponsor will finalize and sign this document prior to locking the database and unblinding (see [Section 2.5](#)). Many of the analyses described in this SAP are quite complex. A blinded team of clinicians and statisticians will review the data carefully to develop conventions and analytic methods not anticipated in writing this SAP.

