**Table 3. Other Efficacy Endpoints**

| Endpoint  | Approach to Analysis   | Comments   |
|---|--|--|
| Hb endpoints – Section 6.3.2  |  |  |
| Change in average Hb value between Baseline and the combined primary efficacy period (PEP) and secondary efficacy periods (SEP) (Weeks 24-52) | Analysis of covariance (ANCOVA) stratified by baseline strata. | Average may include imputed values for PEP and/or SEP.   |
| Having Hb values in the geography-specific target range during PEP or SEP (2 alternate definitions)   | Mantel-Haenszel test stratified by the baseline strata         | This analysis includes the observed hemoglobin values.   |
| CI-0014 only: Hb increase of >1.0 g/dL from Baseline to any time before Week 52   | Mantel-Haenszel test stratified by baseline strata             | This analysis includes the observed hemoglobin values.   |
| CI-0014 only: Time to achieve Hb increase of >1.0 g/dL from Baseline Hb (censored at Week 52)   | Time – to – event  | This analysis will use only observed data.   |
| Progression of CKD ( Section 6.3.6 )  |  |  |
| Progression of CKD (entire length of study)   | Time – to – event  |  |
| Iron endpoints ( Section 6.3.3 )  |  |  |
| Receipt of at least 1 administration of elemental iron ( IV, or oral)   | Mantel-Haenszel test stratified by baseline strata             |  |
| Average weekly dose of elemental iron, IV, or oral  | ANCOVA stratified by baseline strata.                          | If the distribution is highly skewed either because of a large spike at zero or a long tail to the right (or both), other methods may be considered. |

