## **B.3. Primary Efficacy Analysis**

The primary efficacy analysis is based on the difference between the changes from baseline (average pretreatment Hb) to the PEP (average of up to 4 per-visit observations in Weeks 24 to 36). The noninferiority analysis is based on a margin of -0.75 g/dL applied to the difference in mean change between vadadustat and darbepoetin alfa. To establish noninferiority, the lower limit of the confidence interval of the mean change in vadadustat minus the mean change in darbepoetin alfa must be -0.75 g/dL or higher. ANCOVA with multiple imputation for missing data will be used to calculate the 95% confidence interval of the difference.

Multiple imputation will rely on the method of fully conditional specification (FCS). Under this assumption, data for each variable with missing values will be imputed with a separate regression model allowing for all available data to be used in the imputation process. For continuous variables, the regression method will be used for imputations. For categorical variables, logistic regression models will be used for binary outcomes, ordinal logistic regression for ordinal responses, and nominal response logistic regression for nominal responses. The models for imputation under each of these conditions will be described in this appendix.

The output from the multiple imputation procedure is M complete datasets. For the primary analysis, these datasets are analyzed using ANCOVA and the code in [Exhibit B 2](#) below. The M estimates of the difference in the change from baseline in the PEP are then “combined” using PROC MIANALYZE to obtain a final estimate and its associated significance level.

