### Exhibit B 1. SAS Code for Standard Imputation of Missing Values for the Primary Efficacy Analysis

---

```

proc mi data=&INDAT. nimpute=&M. seed=&SEED1. out=&OUTDAT.;
  by TRT;
  class &BINVARS. &NOMVARS. &ORDVARS.;

  var
    STRAT2_HF STRAT3_REG
    SEX RACE AGE HX_CV4 HX_CV_OTH HX_DM ESA_BL SMOKE_BL
    HEP_BL FERR_BL TIBC_BL CRP_BL TSAT_BL HB_BL
    HB_1 HB_2 HEP_3 FERR_3 TIBC_3 CRP_3 TSAT_3
    HB_3 HB_4;
  /* continuous - primary */
  fcs plots=trace reg ( HB_3) nbiter=40;

  /* continuous example - other */
  fcs reg ( HB_1) nbiter=40;

  /* binary or ordinal example */
  fcs logistic( SEX / link=logit likelihood=augment) nbiter=40;

  /* nomial example */
  fcs logistic (RACE/link=glogit likelihood=augment) nbiter=40

  run;

```

---

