**Exhibit B 5. SAS Code to Obtain the Mantel-Haenszel Estimate of Risk Difference**

---

```

*** compute the MH estimate;
proc freq data=&OUTDAT2.;
  by _IMPUTATION_;
  tables STRAT1*STRAT2*STRAT3*TRT*&OUTCOME/riskdiff(common) cmh;
  ods output CommonPdiff=CommonPdiff;

run;

*** combine the results;
proc mianalyze data= CommonPdiff;
  modeleffects Value;
  stderr;
  ods output parameterestimates=MI_SEC;

run;

```

---

Multiple imputation is not currently planned for the other efficacy analyses, except in the case that outcomes for these analyses are part of the multiple imputation for the primary efficacy analysis. If analysis of a covariate included in the overall imputation model (Table B 1) is desired, follow the procedure for the primary or secondary analyses, depending on the variable type.

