### Exhibit C 1. SAS Code for Primary Analysis

---

```
proc genmod data=&OUTDAT2.;
    class TRT (ref="DARB") STRAT1 STRAT2 ;
    model DELT_HB3=HB_BL STRAT1 STRAT2 TRT
        / alpha=0.05 cl diagnostics residuals ;
    estimate "Primary Efficacy" TRT 1 -1;
    lsmeans TRT / cl pdiff cov;
    ods output diffs = MI_ESTIMATES lsmeans=MI_ESTIMATES2;

run;
```

---

The confidence limits for the coefficient associated with TRT in the above model are used to compute the confidence intervals based on M imputed datasets.

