### Exhibit D 2. SAS Code for Analyzing Count Endpoints

---

```
proc genmod data=&INDAT.;
class TRT (ref="DARB") STRAT1 STRAT2;
model COUNT = TRT HB_BL STRAT1 STRAT2 / dist=zip
                                offset=LN_FUT;

zeromodel;
output out=ZIP predicted=PRED pzero=PZERO;
estimate "Treatment Effect" TRT 1 -1 @ZERO TRT 1 -1;
ods output modelfit=FIT estimates=ZIPEST;
run;
```

---

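### Exhibit D 1, and Exhibit C 1 as the non-imputed option under C.1.4, name the stack of 100 imputed datasets with no BY statement or pooling, against the SAP's own text; as printed, the standard errors are 10 times too small

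*SAP*

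**What the plan says.** **How the file is made.** Exhibit B 1 runs the imputation as "proc mi data=&INDAT. nimpute=&M. seed=&SEED1. out=&OUTDAT", and B.1 sets M to 100. B.3 describes the result: "The output from the multiple imputation procedure is M complete datasets". The data step in Exhibit B 2 reads that output and writes `&OUTDAT2.`, which therefore holds 100 records per subject.

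**Where it is used correctly.** Exhibit B 2 fits the primary model separately by imputation, and Exhibit B 3 pools the results. Exhibit B 5 runs a stratified `PROC FREQ` on `&OUTDAT2.` with "by _IMPUTATION_" and then `PROC MIANALYZE`.

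**Where it is not.** Exhibit D 1 repeats the table request of Exhibit B 5 on the same file, "proc freq data=&OUTDAT2", without the BY statement or the pooling step. Exhibit C 1 opens with "proc genmod data=&OUTDAT2", also without BY. C.1.4 offers Exhibit C 1 or Exhibit B 2 according to whether multiple imputation is used, which makes C 1 the non-imputed choice.

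**What the text asks for.** For the two alternate Hb-in-range definitions, Table 3 says: "This analysis includes the observed hemoglobin values". Section 10.2 rules out imputation for the Hb safety endpoints and refers to Appendix D for their intervals. B.5 plans no multiple imputation for the other efficacy analyses, except for outcomes that are already part of the primary imputation. C.1.4 wants one ANCOVA on observed data for variants that are not imputed.

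**The concern.** Section 1 of the SAP gives its code formal standing: "This SAP contains language and programming code that specifies the exact intent of each analysis". Here the code and the text disagree. A single pass over the stack is neither an observed-data analysis nor a valid multiple-imputation analysis.

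The endpoints sent to Exhibit D 1 are the alternate Hb-in-range definitions, iron receipt, transfusion, ESA rescue, any rescue, high and low Hb excursions, and rapid Hb rise. Those sent to Exhibit C 1 under C.1.4 are the non-imputed continuous endpoints, such as iron dose and the iron markers. With intervals a tenth of their proper width, a chance imbalance in transfusion, rescue or Hb excursions would look like a firm difference between the arms. The missing BY statement is not a syntax error, so the program need not fail.

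**Working it through.** **Inputs**

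- M = 100 (B.1).
- 925 subjects per arm (Section 2.6), so 1,850 subjects become 185,000 records.
- 12 strata: 3 regions × 2 NYHA classes × 2 entry-Hb levels (Section 2.1).
- Margin of -15 points for the first four endpoints in D.1.
- Event proportions are not given in the documents. I assume 40% for the worked example and show 20% to 90% as a range.

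**The plan's own figure.** The SAP states no interval width for these endpoints. The nearest stated figure is power above 90% for the primary comparison. SE = 1.5 × √(2/925) = 0.0697 and 0.75/0.0697 − 1.96 = 8.8, so power is effectively 100% and the statement is true. This point does not touch it.

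**Effect of stacking.** Copying every record M times multiplies all cell counts by M and leaves the estimate unchanged, so SE(stacked) = SE/√M = SE/10. This is exact for variables that do not differ between imputations. A simulated trial of 925 per arm, stacked 100 times, gave:

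| Quantity | One record per subject | Stacked | Ratio |
|---|---|---|---|
| SE, Mantel-Haenszel risk difference, 12 strata | 0.02253 | 0.002253 | 10.0 |
| SE, ANCOVA treatment coefficient | 0.0597 | 0.00597 | 10.0 |

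Clopper-Pearson and raw odds-ratio limits shrink by about 10:

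| Quantity | Ratio of interval widths |
|---|---|
| Clopper-Pearson, 9/925 | 10.9 |
| Clopper-Pearson, 463/925 | 10.1 |
| Odds ratio, 100/925 in each arm | 10.1 (0.746–1.341 becomes 0.971–1.030) |

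**Interval width.** For a common proportion p, SE = √(2p(1−p)/925).

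| p | Proper 95% half-width (points) | Stacked |
|---|---|---|
| 0.2 | 3.65 | 0.36 |
| 0.5 | 4.56 | 0.46 |
| 0.9 | 2.73 | 0.27 |

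**Error rates.** The printed limits sit at 1.96/10 = 0.196 true standard errors. Coverage is 2Φ(0.196) − 1 = 15.5%. Two-sided rejection of zero difference when there is none is 1 − 0.155 = 84.5%.

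**Effect on the -15-point rule.** At p = 0.4, SE = √(2 × 0.4 × 0.6/925) = 2.28 points.

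- Proper interval: passes if the observed difference is above −15 + 1.96 × 2.28 ≈ −10.5.
- Stacked interval: passes if it is above −15 + 0.196 × 2.28 ≈ −14.6.

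The verdict differs only between those two values. At no difference both intervals pass.

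**Which file the text needs.** Table B 1 carries Hb as period averages. The alternate definitions count individual readings in range, so they cannot be derived from the imputed averages and need observed data. Hepcidin, ferritin, TIBC and TSAT in the primary period are in Table B 1. On the stack their gaps would be filled with imputed values, although Table 3 specifies observed data only.

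**The case against.** The strongest defence is that `&OUTDAT2.` is a macro placeholder and the exhibits are templates. Exhibits B 1 and B 4 write different content to the same name, `&OUTDAT.`. Appendix C introduces its code as examples, C.1.1 calls Exhibit C 1 basic and refers to Exhibit B 2 for the full process, and D.1 calls Exhibit D 1 a structure. B.2 allows small changes to code. The text already rules out the stacked analysis for most of these endpoints, and 185,000 records would be hard to miss.

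Much of this stands. A reader might infer that the sponsor plans to count each subject 100 times. The documents do not support that: this is a wrong or reused dataset name that conflicts with the text. The Exhibit C 1 limb is the weaker one, because C.1.4 states the observed-data intent directly.

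It does not dispose of the point. Nothing redefines `&OUTDAT2.`, and the other exhibits do separate their files: Exhibit D 2 uses "proc genmod data=&INDAT", Exhibit C 2 uses `&LONGDAT.` and Exhibit D 3 uses `&TTEDAT.`. The allowance in B.2 concerns software updates and fit to the data. Because of the exception in B.5, the right file is not self-evident for every endpoint.

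**Conclusion.** The conflict between code and text is real, and the factor of 10 is correct for the code as printed. It is conditional on that code being run on the file that Exhibit B 2 defines.

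Three wider conclusions are tempting but not supported:

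- **That every confidence interval in the plan is too narrow.** The primary and key secondary Hb analyses (Exhibits B 2 and B 3) and the two average-Hb-in-range endpoints (Exhibit B 5) are processed by imputation and pooled. Exhibits C 2, D 2 and D 3 name other files, and MACE has its own SAP.
- **That all noninferiority conclusions in D.1 are unreliable.** The rule covers four endpoints, and its verdict changes only for observed differences between about −10.5 and −14.6 points (40% event rate, 925 per arm). The 84% figure is for a test of zero difference.
- **That false superiority claims would follow in D.1.** D.1 has no superiority rule. Those for the target range are in Sections 9.3.1 and 9.3.2, which use Exhibit B 5.

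Section 9.3 calls the other efficacy endpoints exploratory, C.1.3 treats the other continuous endpoints as descriptive, and Section 10 makes most safety analyses descriptive. The weight is therefore moderate: correct it before database lock, but no primary, key secondary or MACE conclusion depends on it.

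**What to change.** In Exhibit D 1, and in Exhibit C 1 as used under C.1.4, replace `&OUTDAT2.` with the observed one-record-per-subject dataset, for example `&INDAT.` as in Exhibit D 2. Where an endpoint is meant to use imputed values under the exception in B.5, add `BY _IMPUTATION_` and the `PROC MIANALYZE` step as in Exhibit B 5. State endpoint by endpoint, for instance in an extra column of Table 3, which of the two applies. The cost is a few lines of code and a short table edit, with no effect on design, data collection or sample size.

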## D.2. Analysis of Count Data

This section describes the methods for analyzing endpoints measured as counts. These endpoints include:

- Number of ESA episodes
- Number of RBC transfusion episodes

The initial analysis approach will be descriptive, reporting the proportion of subjects with counts greater than 0 and the mean number for this population. Statistical modeling based on a zero-inflated Poisson regression model, as outlined in [Exhibit D 2](#), will be used to account for stratification factors.

### Exhibit D 2. SAS Code for Analyzing Count Endpoints

---

```
proc genmod data=&INDAT.;
class TRT (ref="DARB") STRAT1 STRAT2;
model COUNT = TRT HB_BL STRAT1 STRAT2 / dist=zip
                                offset=LN_FUT;

zeromodel;
output out=ZIP predicted=PRED pzero=PZERO;
estimate "Treatment Effect" TRT 1 -1 @ZERO TRT 1 -1;
ods output modelfit=FIT estimates=ZIPEST;
run;
```

---

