### 6.3.7 Endpoints Related to RBC Transfusion

These endpoints address RBC transfusion for the entire length of study, by the four analysis time periods in Year 1 (see [Section 5.1](#)), and in the long-term treatment/follow-up period (Week 52 to EOS) unless otherwise specified.

- Receipt of any RBC transfusion
- Time to first RBC transfusion (for entire study)
- Total number of RBC transfusion episodes received
- Rate of RBC transfusions, calculated as the number of episodes divided by the duration of at-risk follow-up in person-years

RBC transfusion may be considered rescue when “Worsening Anaemia due to CKD” is the reason indicated on the CRF.

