## 9 EFFICACY ENDPOINTS AND ANALYSES

This section briefly describes the methods to be used for each of the efficacy endpoints. Rather than providing details for each endpoint, the accompanying Appendices describe the approaches to be used for specific types of data. For all the models and methods described below, see [Appendix B](#) for handling of any missing data.

The general approach to analysis of continuous outcomes will be analysis of covariance (ANCOVA) with multiple imputation for missing data or mixed models for repeated measurements (MMRM) on observed data. For a description of the models to be used, see [Appendix C](#).

For binary variables, the general approach will be Mantel-Haenszel estimation of risk difference stratified ([Mantel, 1954](#)) by the baseline strata with (or without) multiple imputation to deal with missing data. See [Appendix D](#).

Some endpoints come from count data (e.g., the number of RBC transfusions) that are likely to have a spike at zero and a long tail. Such data are often complicated to analyze because of their highly skewed distributions. While the samples sizes are so large that the Central Limit Theorem ensures that the means of these distributions are essentially normal, some interpretation of the nature of the distributions may be useful clinically. To the extent reasonable, we have described the planned methods for such data, but ad hoc methods may be necessary if the skewness is extreme. See [Appendix D](#) for the general approach.

For time-to-event variables, the general approach will be to use Cox models stratified by the baseline randomization strata. See [Appendix D](#).

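### The episode-count code requests a treatment contrast in a zero part that has no treatment term, and the Poisson part makes no allowance for extra variation among at-risk subjects

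*SAP*

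**What the plan says.** SAP Appendix D.2 covers two counts: ESA episodes and "Number of RBC transfusion episodes". It starts descriptively, "reporting the proportion of subjects with counts greater than 0 and the mean number for this population". It then specifies "Statistical modeling based on a zero-inflated Poisson regression model", with the code in Exhibit D 2.

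The count part of the exhibit is "model COUNT = TRT HB_BL STRAT1 STRAT2 / dist=zip", with log follow-up time as offset. ZEROMODEL follows with nothing after it. The ESTIMATE statement then asks for "TRT 1 -1 @ZERO TRT 1 -1", that is, a treatment contrast in both parts. D.2 names no negative binomial alternative, scale parameter or robust variance.

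Three other places bear on this:
- SAP Section 9 expects counts "that are likely to have a spike at zero and a long tail" and allows ad hoc methods for extreme skewness. Table 3 likewise allows other methods. Neither names one.
- SAP 6.3.7 lists a separate summary: "Rate of RBC transfusions, calculated as the number of episodes divided by the duration of at-risk follow-up in person-years".
- SAP 9.3 calls these endpoints exploratory and does not correct them for multiplicity.

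**The concern.** A zero part with no effects is an intercept only, so one structural-zero probability serves both arms. The single treatment coefficient is then a rate ratio among subjects taken to be at risk. It is not the ratio of the episode rates that 6.3.7 describes. If treatment changes who needs transfusion rather than how often those subjects are transfused, the model has nowhere to put the effect.

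Separately, zero inflation deals with the spike at zero but not with the long tail. Among at-risk subjects the model fixes the variance equal to the mean. If some subjects are transfused repeatedly and others once, the standard error of the treatment contrast is understated.

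This is the only model in the plan that compares repeat transfusion or ESA use between arms. A wrong contrast here would misstate the burden of rescue.

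**Working it through.** The documents give no rate, dispersion or power for these counts, so there is no figure of the plan's own to reproduce. The check is a reading of the code followed by simulation.

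**Inputs.** From the SAP: 925 per arm (2.6), 1:1 allocation (2.1) and the model form (Exhibit D 2). Assumed: share at risk π, mean count among those at risk μ, gamma dispersion α, equal follow-up and no baseline covariates. The test is a 2-sided 5% Wald test, with 1,000 simulated trials per scenario in the tables.

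**Step 1: treatment changes only who is at risk, with Poisson counts.** The marginal mean is πμ, so the true rate ratio is π_vad / π_darb. For example, 0.14 × 3 / (0.20 × 3) = 0.70. The expected share with any episode is π(1 − e^−μ). For μ = 1.5 that is 0.20 × 0.777 = 15.5% against 0.14 × 0.777 = 10.9%.

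| At risk, darbepoetin v vadadustat | μ | True ratio | Exhibit D 2 ratio (median) | Power, D 2 contrast | Power, any v none |
|---|---|---|---|---|---|
| 20% v 14% | 1.5 | 0.70 | 0.87 | 24% | 85% |
| 20% v 14% | 3 | 0.70 | 0.97 | 7% | 90% |
| 30% v 22% | 2 | 0.73 | 0.92 | 17% | 94% |
| 40% v 30% | 2 | 0.75 | 0.93 | 22% | 98% |

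A further simulation set added a negative binomial model:
- At risk 20% v 30%, μ = 2, true ratio 0.30/0.20 = 1.50. Exhibit D 2 gave 1.10 with 23% power; negative binomial gave 1.49 with 93%.
- At risk 20% v 14%, μ = 3, true ratio 0.70. Exhibit D 2 gave 0.98 and rejected in 5% of trials; negative binomial gave 0.70 with 63% power.

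**Step 2: no treatment effect, with extra variation among at-risk subjects.** With gamma mixing, the at-risk variance is μ + αμ². At μ = 2 this is 4, 6 and 10 for α = 0.5, 1 and 2, where the Poisson part assumes 2.

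| Scenario | α | Median model SE | Empirical SD | Null rejection |
|---|---|---|---|---|
| 30% at risk, μ = 2 | 0 | 0.070 | 0.071 | 6.0% |
| 30% at risk, μ = 2 | 0.5 | 0.068 | 0.087 | 11.9% |
| 30% at risk, μ = 2 | 1 | 0.066 | 0.103 | 19.6% |
| 30% at risk, μ = 2 | 2 | 0.064 | 0.120 | 30.3% |
| All at risk, μ = 0.5 | 0.5 | 0.071 | 0.076 | 5.6% |
| All at risk, μ = 0.5 | 1 | 0.075 | 0.081 | 6.7% |
| All at risk, μ = 0.5 | 2 | 0.079 | 0.095 | 11.1% |

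In the worst row the model SE is 0.064/0.120 = 53% of the true spread. Without structural zeros the damage is smaller, because the zero-inflation term absorbs much of the dispersion.

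**Step 3: does adding TRT to the zero part repair it?** It repairs the contrast. In the Step 1 scenarios the zero-part treatment test has 78% to 97% power, and the joint 2-df likelihood-ratio test 77% to 96%. It does not repair the variance. With 30% at risk and α = 0.5, 1 and 2, the joint test still rejects a true null in 10%, 17% and 25% of trials. A negative binomial model rejected in 2% at α = 1 in that setting.

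**The case against.** The strongest reply is that the trial's read-out on needing transfusion does not depend on this model. Receipt of any RBC transfusion, any ESA rescue and any rescue therapy are compared by stratified Mantel-Haenszel methods (SAP Table 3, D.1). Time to first transfusion has its own Cox model (D.3). A reader might infer that the plan would miss an effect on needing any transfusion; the documents do not support that. In the Step 1 scenarios a simple any-versus-none comparison has 85% to 98% power. This part of the reply stands.

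Three other strong readings also fail:
- That the model allows no overdispersion. A zero-inflated Poisson has marginal variance above its mean; what it lacks is extra variation among at-risk subjects.
- That its standard errors are always too small. They are right when at-risk counts are Poisson. SAP 6.3.1 also merges transfusions up to 7 days apart and ESA doses up to 30 days apart into one episode, which removes short-interval clustering. Differences between subjects may remain.
- That the 6.3.7 rate becomes unobtainable. It can be tabulated directly from episodes and person-years.

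It can also be said that the ESTIMATE line shows TRT was meant to be in ZEROMODEL, and that the slip would surface when the code is run. That is plausible. But SAP Section 1 says the code gives the exact intent of each analysis, so it should be right before lock. Adding TRT also leaves the variance problem. The fallbacks in Section 9 and Table 3 name no method and no trigger, so they do not settle it.

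**Conclusion.** The concern holds for the count model, not for the plan as a whole. Exhibit D 2 is internally inconsistent. As coded, its treatment contrast can shrink a true rate ratio of 1.5 to about 1.1, or move a true 0.70 to about 0.98, when the effect lies in who is at risk. Null rejection at a nominal 5% runs from about 6% to 30% over assumed dispersions of 0.5 to 2, depending on whether structural zeros are present.

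These sizes rest on assumed rates and dispersion, equal follow-up and no covariates. The long tail the SAP expects makes extra dispersion plausible, but nothing in the documents measures it. That an empty ZEROMODEL means intercept-only, and that the zero-part contrast would not be estimable, is a reading of the code; SAS was not run. No formal conclusion depends on these exploratory endpoints, but the fix is cheap enough to be worth making.

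**What to change.** Before database lock, analyse the episode counts by negative binomial regression with log follow-up time as offset and treatment, baseline Hb and the stratification factors as predictors. Report the rate ratio with its 95% CI.

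If the zero-inflated model is kept, put TRT in ZEROMODEL, report both parts, and use a zero-inflated negative binomial or a robust variance. Adding TRT alone does not correct the standard errors. Those two variance options were not simulated here.

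The cost is one paragraph in D.2 and a few lines in Exhibit D 2. No data collection changes.
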